#### 2.1.4 Safety endpoints

The safety endpoints are assessed by:

- Adverse events (AEs), serious adverse events (SAEs), AE of special interest (AESIs), hypoglycemia (severe, documented, asymptomatic, probable, relative), vital signs, ECG changes, and safety laboratory values,
- Change of heart rate from baseline to Week 26 by ECG,
- Change of heart rate from baseline to Week 26 by Holter monitor in up to 50% subset of all patients,
- Antibody assessments: anti-SAR425899 antibodies samples will be collected in all patients (except patients on Liraglutide) at baseline, Week 2, Week 4, Week 14, and Week 26 before dosing. Patients will be asked to provide sample for anti-SAR425899 antibodies assessments 3 months after the end of the study if needed.

#### *Observation period*

The observation period will be divided into 4 epochs:

- The **screening** epoch is defined as the time from the signed informed consent date up to the first administration of the IMP.
- The **treatment** epoch is defined as the time from the first administration of the IMP to the last administration of the IMP
- The **residual treatment** epoch is defined as the time from the last administration of the IMP up to 3 days (1 day for hypoglycemia, 28 days for anti-SAR425899 antibody) after the last administration of IMP.

The treatment-emergent adverse event (TEAE) period will include both **treatment** and **residual treatment** epochs.

- The **posttreatment** epoch is defined as the period of time starting the day after the end of the treatment-emergent adverse event period up to the end of the study (defined as last protocol-planned visit or the resolution/stabilization of all serious adverse events (SAE) and adverse events with prespecified monitoring as defined in protocol).

The on-study observation period is defined as the time from the start of treatment until the end of study (defined as the last scheduled visit for those who completed the study and the date collected on e-CRF page “Completion of End of Study/Follow-up” for those who did not complete the study, or the resolution/stabilization of all serious adverse events and adverse events with prespecified monitoring as defined in the protocol whichever is the latest).

### **2.1.4.1 Hypoglycemia**

Hypoglycemia will be identified as events recorded on the dedicated eCRF or eDiary “Hypoglycemic Event Information” page, and will be categorized as follows (see study protocol for further details):

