9.2.1.2.3 Self-monitored plasma glucose profiles

The 7-point SMPG profile should be measured at the following 7 points: preprandial and 2 hours postprandial for breakfast, lunch, dinner and at bedtime. Two hours postprandial (breakfast, lunch and dinner) is defined as 2 hours after the start of the meal.

The patients are requested to perform 7-point SMPG profile measurement over a single 24-hour period in the week before Visit 4 (Week 0), Visit 10 (Week 14), and Visit 12 (Week 26, end of treatment assessment visit). All SMPG values measured on these days will be recorded with a glucometer provided by the Sponsor.

9.2.1.2.4 *Body weight*

Body weight should be obtained with the patient wearing undergarments or very light clothing and no shoes, and with an empty bladder in fasting conditions, in the morning before breakfast. The same scale should be used throughout the study, and calibrated on a regular basis as recommended by the manufacturer. The use of balance scales is recommended; if digital scales are used, testing with standard weights is of particular importance. The floor surface on which the scale rests must be hard and should not be carpeted or covered with other soft material. The scale should be balanced with both weights at zero and the balance bar aligned. The patient should stand in the center of the platform as standing off-center may affect measurement. The weights are moved until the beam balances (the arrows are aligned). The weight is read and recorded in the eCRF and source data. Self-reported weights are not acceptable; patients must not read the scales themselves.

Body weight will be measured on days indicated in the flow chart (see [Section 1.2](#)). Weight should be measured in the fasting state in the morning at approximately the same time with an empty bladder, without shoes and only wearing undergarments or light clothing. Weight measured at screening Visit 1 will be used only for calculation of screening BMI for eligibility criteria whereas weight measured at Visit 4 will be used as baseline for assessment of change in body weight and for calculation of baseline BMI which will be the BMI value used for stratification.

9.2.1.2.5 *Blood glucose, insulin, and C-peptide*

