- **Relative hypoglycemia:** Relative hypoglycemia recently termed “pseudo-hypoglycemia” is an event during which the person with diabetes reports any of the typical symptoms of hypoglycemia, and interprets the symptoms as indicative of hypoglycemia, but with a measured plasma glucose concentration greater than 70 mg/dL (3.9 mmol/L), but approaching this level.

Patients will be instructed to measure finger stick plasma glucose levels prior to the administration of carbohydrates whenever symptomatic hypoglycemia is suspected, unless safety considerations necessitate immediate glucose rescue prior to confirmation, and then a glucose measurement should be performed as soon as safe, with appropriate diary documentation. Details on hypoglycemia episodes will be captured in the patient diaries, and patients will contact the sites as soon as possible following severe events to review the details and decide on any necessary measures to be taken.

Symptomatic hypoglycemia episodes will be documented on the dedicated hypoglycemia event page in the eCRF. Symptomatic hypoglycemia events fulfilling the criteria of a SAE will also be documented on AE and SAE forms form in the eCRF.

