11.4.3.1 Analyses of hypoglycemia

The number (%) of patients and rate in patient years (2 types: the number of patients with events or the total number of events per 100 patient-year) of each type of hypoglycemia (severe, documented, asymptomatic, probable and relative hypoglycemia) will be summarized by treatment group. The pattern of symptomatic hypoglycemia occurrence over time will also be assessed, as appropriate. An overall hypoglycemia (includes severe, documented, asymptomatic, probable and relative) table will also be provided.

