### **2.1.3 Efficacy endpoints**

All biological efficacy assessments will be performed by a central laboratory. All scheduled measurements collected during the study will be used in the analysis, including those obtained after IMP discontinuation or rescue medication use.

Efficacy variables will be summarized in both standard international units and conventional units when applicable.

The baseline value for efficacy endpoints is the last available value prior to the first injection of IMP or the last available value on or before the date of randomization if not treated with IMP.

HbA1c is assayed at screening (Visit 1); at Visit 4 (Day 1) before first IP injection; at Visit 6 (Week 2); at Visit 8 (Week 4); at Visit 9 (Week 8); at Visit 10 (Week 14); at Visit 11 (Week 20); and at final assessment (Visit 12 at Week 26, primary endpoint assessment visit).

Body weight is measured at screening (Visit 1); at Visit 4 (Day 1) before first IP injection; at Visit 6 (Week 2); at Visit 8 (Week 4); at Visit 9 (Week 8); at Visit 10 (Week 14); at Visit 11 (Week 20); and at final assessment (Visit 12 at Week 26, primary endpoint assessment visit).

FPG is measured at a central laboratory at screening (Visit 1); at Visit 4 (Day 1) before first IP injection; at Visit 6 (Week 2); at Visit 8 (Week 4); at Visit 9 (Week 8); at Visit 10 (Week 14); at Visit 11 (Week 20); and at final assessment (Visit 12 at Week 26, primary endpoint assessment visit).

The self-monitored plasma glucose (SMPG) is measured over a single 24-hr period in the week before Visit 4 (Day 1) before first IP injection, Visit 10 (Week 14), and Visit 12 (Week 26, primary endpoint assessment visit).

Fasting insulin are measured at Visit 4 (Day 1) before first IP injection; at Visit 10 (Week 14); and at final assessment (Visit 12 at Week 26, primary endpoint assessment visit).

Following list of standardized meal test related measurements at premeal, 10 min, 20 min, 0.5 h, 1 h, 1.5 h, 2 h, 3 h, 4 h post meal at Visit 3 (Week -1); and at final assessment (Visit 12 at Week 26, primary endpoint assessment visit) in up to 50% subset of all patients:

- post-prandial plasma glucose (PPG) and associated glucose excursion
- postprandial insulin, proinsulin and C-peptide and associated excursion values

Pre-meal measurements of pro-insulin and C-peptide from the meal test will be used as fasting pro-insulin, and C-peptide values.

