### **Asymptomatic hypoglycemia**

Asymptomatic hypoglycemia: Asymptomatic hypoglycemia is an event not accompanied by typical symptoms of hypoglycemia but with a measured plasma glucose concentration less than or equal to 70 mg/dL (3.9 mmol/L).

- not ticked “Subject was Not Capable of Treating Self and Required Assistance” to the question “Countermeasure Administration” and
- ticked “No” to the question “Were Symptoms Present” and
- with a measured plasma glucose value  $\leq 70$  mg/dL (3.9 mmol/L).

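### SAP drops the separate by-arm tables for asymptomatic, probable and relative hypoglycemia that the protocol requires, and its filed-events rule leaves no sure route for symptom-free low values at scheduled, largely masked, glucose measurements

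*SAP*

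**What the plan says.** **Tables.** Protocol 11.4.3.1 says that "each type of hypoglycemia (severe, documented, asymptomatic, probable and relative hypoglycemia) will be summarized by treatment group", with patient numbers, percentages and two kinds of rate, plus an overall table covering all five types. SAP 2.4.5.1 classifies events into the same five types. Its by-arm summaries with incidence rates, however, are for any, severe and documented symptomatic hypoglycemia only. It adds a listing in which each event carries its category. The log of SAP changes (SAP 1.6, Table 2) does not mention the difference.

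**Source of events.** SAP 2.1.4.1: "Hypoglycemia will be identified as events recorded on the dedicated eCRF or eDiary" page for hypoglycemic event information. The SAP defines asymptomatic hypoglycemia as "an event not accompanied by typical symptoms of hypoglycemia but with a measured plasma glucose concentration less than or equal to 70 mg/dL", identified by a No to the symptoms question together with such a value. Protocol 10.6.1 says "Symptomatic hypoglycemia episodes will be documented on the dedicated hypoglycemia event page in the eCRF" and gives no matching eCRF instruction for asymptomatic episodes. It also says, without limiting this to symptomatic episodes, "Details on hypoglycemia episodes will be captured in the patient diaries".

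**Visibility of glucose values.** Protocol 8.3.1 withholds post-baseline FPG and meal-test results from the investigator and sponsor until Week 26 or the end-of-treatment visit. The only laboratory alert it describes is for values above the rescue thresholds. SAP 2.4.5 (general common rules) provides no summaries of potentially clinically significant abnormalities (PCSA) for laboratory parameters that are efficacy endpoints, and it names plasma glucose among them.

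**The concern.** Hypoglycemia by type is a named safety endpoint in both documents (Protocol 9.2.2, SAP 2.1.4). If three of the five types have no row of their own, a reader of the study report cannot see by arm how often each occurred without re-tabulating the listing. The any-hypoglycemia row does not replace them. It pools relative events, where glucose was above 70 mg/dL, with asymptomatic events, where it was at or below 70 mg/dL.

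The source rule matters most for the asymptomatic type. A symptom-free low is found only by measuring, and Protocol 10.6.1 prompts extra finger-stick testing when symptoms are suspected. Scheduled measurements are therefore the main place where such a value would appear. Under SAP 2.1.4.1 it counts only if someone also files an event. For masked values, nobody at the site has the result when it arises.

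**Working it through.** The documents give no figure to reproduce on this point. The check compares the two table plans, traces each kind of reading, and counts readings.

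**1. Table plans side by side**

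| Type | Protocol 11.4.3.1 | SAP 2.4.5.1 |
|---|---|---|
| Severe | own summary | own summary |
| Documented symptomatic | own summary | own summary |
| Asymptomatic | own summary | listing flag only |
| Probable symptomatic | own summary | listing flag only |
| Relative | own summary | listing flag only |
| Overall / any | table | table |

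Three of five types lose their own summary. Subtraction does not recover them. If any hypoglycemia is the union of the five types, events of any type minus severe minus documented gives asymptomatic, probable and relative combined. Patient counts cannot be subtracted at all, because one patient may have several types.

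**2. Inputs for the count of scheduled on-treatment readings**

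- FPG (SAP 2.1.3): Weeks 2, 4, 8, 14, 20 and 26, so 6 values.
- Self-measured profile (SMPG; Protocol 9.2.1.2.3): "should be measured at the following 7 points: preprandial and 2 hours postprandial for breakfast, lunch, dinner and at bedtime", done "over a single 24-hour period in the week before Visit 4 (Week 0), Visit 10 (Week 14), and Visit 12 (Week 26", end of treatment). Two of these days are on treatment, so 2 × 7 = 14 values.
- Meal test (Protocol 9.2.1.2.2): premeal plus 8 post-meal samples at Week 26, so 9 values, in up to 50% of patients.

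Per completer: 6 + 14 = 20 readings, or 20 + 9 = 29 in the meal-test subset.

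For 270 patients with full follow-up:

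- FPG: 270 × 6 = 1,620
- SMPG: 270 × 14 = 3,780
- FPG plus SMPG: 1,620 + 3,780 = 5,400
- Meal test: at most 135 × 9 = 1,215
- All: 5,400 + 1,215 = 6,615
- FPG plus meal test: 1,620 + 1,215 = 2,835

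These are ceilings on readings. The hypoglycemia window closes 1 day after the last dose (SAP 2.1.4), so later readings drop out.

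**3. Where a symptom-free value of 70 mg/dL or less would go**

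| Reading | Seen by patient or site at the time? | Rule requiring it to be filed? | PCSA table? |
|---|---|---|---|
| SMPG (14) | yes, sponsor's glucometer | none stated | no |
| Central FPG (6) | no, masked; high-value alert only | none stated | no |
| Meal-test glucose (9, subset) | no, masked | none stated | no |

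Protocol 8.3.1 sets the masking up to Week 26 or end of treatment. It does not make clear when the Week 26 results themselves are released, but release would create no duty to file an event.

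**4. Possible size, by assumption only**

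The documents give no rate of low readings. Let p be the assumed chance that one reading is at or below 70 mg/dL, with independent readings. The chance of at least one such value in n readings is 1 − (1 − p)^n.

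| p | n = 6 (FPG) | n = 20 (FPG + SMPG) | Patients per 60, n = 6 | Patients per 60, n = 20 |
|---|---|---|---|---|
| 0.1% | 0.6% | 2.0% | 0.4 | 1.2 |
| 0.5% | 3.0% | 9.5% | 1.8 | 5.7 |
| 1% | 5.9% | 18.2% | 3.5 | 10.9 |
| 2% | 11.4% | 33.2% | 6.8 | 19.9 |

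These are patients with at least one low reading, not missed events. Some lows would be symptomatic or filed anyway. If lows cluster within patients, fewer patients are affected at the same p.

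**The case against.** The case for leaving the plan alone has real substance.

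- A reader might infer that asymptomatic hypoglycemia vanishes from the results. It does not. Such events count under any hypoglycemia, with rates by arm, and each is flagged in the listing.
- A reader might infer that the event page cannot hold asymptomatic events. The documents do not support that. SAP 2.1.4.1 accepts the eCRF or the eDiary under a neutral page title, and the asymptomatic rule uses a No to the symptoms question. The protocol has episodes captured in diaries. The SAP uses a title limited to symptomatic events only under the severe, documented and probable types.
- A reader might infer that 20 readings per patient, or 5,400 in all, are discarded. But 14 of the 20 are SMPG values that the patient sees, and sites review diary and glucometer use and record hypoglycemic events at on-site visits. The 5,400 counts readings, not lows.
- By-visit summaries of FPG and SMPG report the minimum by arm (SAP 2.5.4), so an extreme low would be visible, though not counted. Patients enter with HbA1c of 7% to 10% on no glucose-lowering drug other than metformin, so lows may be few.
- Asymptomatic hypoglycemia is defined as an event. Turning readings into events needs an episode rule and a rule for linking symptoms.
- SAP Appendix B (summary of analyses) and the eCRF were not in the text available, so a per-type table or a filing instruction there cannot be excluded.

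All of this stands, and it limits the point. It does not remove the mismatch between Protocol 11.4.3.1 and the SAP text, nor supply a rule for unfiled scheduled lows.

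**Conclusion.** The point holds on two counts. The firmer one is that SAP 2.4.5.1 omits separate by-arm summaries for three of the five types the protocol requires, without logging the change. That rests on the text alone, subject to what Appendix B may contain.

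The second is smaller. Under the rule as written, a symptom-free value of 70 mg/dL or less at one of the 6 masked FPG measurements, or among the 9 meal-test samples in the subset, enters neither a hypoglycemia count nor a PCSA table unless an event is filed. For the 14 SMPG values, counting depends on voluntary filing. How many events this misses is unknown; the range in the working rests on assumed rates.

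A reader might also infer that the plan favours one arm, since liraglutide is open-label and the SAR425899 dose level is not blinded. Filing could differ by arm for that reason, but nothing in the documents shows that it does or in which direction.

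**What to change.** Before database lock:

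1. **SAP 2.4.5.1.** Summarise each of the five types by arm, with number, percentage and both rates, alongside the overall table as in Protocol 11.4.3.1.
2. **Event page.** Reconcile Protocol 10.6.1 with SAP 2.1.4.1 on whether the eCRF page takes asymptomatic episodes, and use one page title throughout.
3. **Supplementary derived count, shown apart from filed events.** By arm, give the number of patients with any scheduled SMPG, central FPG or meal-test glucose of 70 mg/dL (3.9 mmol/L) or less, within the hypoglycemia treatment-emergent window and with no linked symptomatic event. Count each patient once; if episodes are also wanted, count at most one per day. State the time window used to link symptoms. Show the three sources separately, with the substudy population as the denominator for meal-test values.
4. **SAP 1.6, Table 2.** Record the added derivation.

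The cost is one derivation on data already scheduled for collection, three restored categories and one extra table. Asymptomatic counts may rise in every arm. Keeping the derived count separate leaves the filed-event results unchanged.

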#### **Severe hypoglycemia**

Severe hypoglycemia is an event requiring assistance of another person to actively administer carbohydrate, glucagon, or other resuscitative actions. These episodes may be associated with sufficient neuroglycopenia to induce seizure, unconsciousness, or coma. Plasma glucose measurements may not be available during such an event, but neurological recovery attributable to the restoration of plasma glucose to normal is considered sufficient evidence that the event was induced by a low plasma glucose concentration.

The definition of severe hypoglycemia includes all episodes in which neurological impairment was severe enough to prevent self-treatment and which were thus thought to place patients at risk for injury to themselves or others.

**Note** that “requires assistance” means that the patient could not help himself or herself. Assisting a patient out of kindness, when assistance is not required, should not be considered a “requires assistance” incident.

Severe hypoglycemia will be qualified as an SAE only if it fulfills SAE criteria. All events of seizure, unconsciousness, or coma must be reported as SAEs.

In the eCRF, severe hypoglycemia is identified based on information captured in the “Symptomatic hypoglycemic event information” page as those

- ticked “Subject was Not Capable of Treating Self and Required Assistance” to the question “Countermeasure Administration” and
- ticked “Yes” to the question “Were Symptoms Present”.

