10.6 SAFETY INSTRUCTIONS

10.6.1 Hypoglycemia

Hypoglycemic events will be categorized as follows:

- Severe hypoglycemia: Severe hypoglycemia is an event requiring third party assistance of another person to actively administer carbohydrate, glucagon, or other resuscitative actions. These episodes may be associated with sufficient neuroglycopenia to induce seizure, unconsciousness or coma. Plasma glucose measurements may not be available during such an event, but neurological recovery attributable to the restoration of plasma glucose to normal is considered sufficient evidence that the event was induced by a low plasma glucose concentration. The definition of severe symptomatic hypoglycemia includes all episodes in which neurological impairment was severe enough to prevent self-treatment and which were thus thought to place patients at risk for injury to themselves or others. Note that "requires third party assistance" means that the patient could not help himself or herself. Assisting a patient out of kindness, when assistance is not required, should not be considered a "requires assistance" incident.

Severe hypoglycemia will be qualified as a SAE only if it fulfills SAE criteria. All events of seizure, unconsciousness, or coma must be reported as SAEs.

- Documented symptomatic hypoglycemia: Documented symptomatic hypoglycemia is an event during which typical symptoms of hypoglycemia are accompanied by a measured plasma glucose concentration of ≤ 70 mg/dL (3.9 mmol/L). Clinical symptoms that are considered to result from a hypoglycemic episode include: increased sweating, nervousness, asthenia/weakness, tremor, dizziness, increased appetite, palpitations, headache, sleep disorder, confusion, seizures, unconsciousness, or coma.

- **Asymptomatic hypoglycemia:** Asymptomatic hypoglycemia is an event not accompanied by typical symptoms of hypoglycemia but with a measured plasma glucose concentration less than or equal to 70 mg/dL (3.9 mmol/L).
- **Probable symptomatic hypoglycemia:** Probable symptomatic hypoglycemia is an event during which symptoms of hypoglycemia are not accompanied by a plasma glucose determination, but was presumably caused by a plasma glucose concentration less than or equal to 70 mg/dL (3.9 mmol/L); symptoms treated with oral carbohydrate without a test of plasma glucose.

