### **2.4.5.1 Analyses of hypoglycemia**

Analyses of hypoglycemia will be performed on the TEAE period, as defined in [Section 2.1.4](#). Hypoglycemia will be classified as severe hypoglycemia, documented symptomatic hypoglycemia, asymptomatic hypoglycemia, probable symptomatic hypoglycemia or relative hypoglycemia (see [Section 2.1.4.1](#)).

The number (%) of patients with any hypoglycemia, severe hypoglycemia and documented symptomatic hypoglycemia will be summarized respectively by treatment group for the TEAE period, as well as the incidence rate in patient years. Two types of incidence rates will be presented: the number of patients with at least 1 event per patient years (calculated as the number of patients with at least 1 event / total exposure in patient years), and the number of events per patient years (calculated as the number of events / total exposure in patient years). Note: here exposure is duration of TEAE period, ie, duration of IMP treatment in days +1 (see [Section 2.1.4](#)).

The summary of frequency and incidence rate in patient years for severe hypoglycemia or documented symptomatic hypoglycemia will be provided as appropriate by gender (Male, Female), age group (<50, ≥50 to <65, ≥65 to <75, ≥75 years of age), race (American Indian or Alaska Native, Asian/Oriental, Black, Native Hawaiian or Other Pacific Islander, White, Other).

The summary of frequency and incidence rate in patient years for severe hypoglycemia or documented symptomatic hypoglycemia will be provided as appropriate by anti-SAR425899 antibody status (Positive, Negative) during TEAE period. A patient is defined as anti-SAR425899 antibody positive during the TEAE period if the patient is anti-SAR425899 antibody positive at any time during TEAE period, ie, duration of IMP treatment in days +28 (see [Section 2.1.4](#)).

A KM curve will also be provided by treatment group for the time to first onset of severe or documented symptomatic hypoglycemia during the TEAE period.

A listing of patients for all hypoglycemic events reported on the dedicated eDiary or eCRF “Hypoglycemic Event Information” form will be provided with each category flagged (ie, severe hypoglycemia, documented symptomatic hypoglycemia, asymptomatic hypoglycemia, probable symptomatic hypoglycemia and relative hypoglycemia).

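### The SAP's rule for severe hypoglycemia also requires symptoms recorded as Yes, so an assisted event with that item answered No or left blank is put in no category

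*SAP*

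**What the plan says.** Protocol 10.6.1 gives the definition: "Severe hypoglycemia is an event requiring third party assistance of another person to actively administer carbohydrate, glucagon, or other resuscitative actions". SAP 2.1.4.1 repeats it almost unchanged: "Severe hypoglycemia is an event requiring assistance of another person to actively administer carbohydrate, glucagon, or other resuscitative actions". The SAP also sets the scope: "The definition of severe hypoglycemia includes all episodes in which neurological impairment was severe enough to prevent self-treatment". Neither text states a separate symptom criterion, although the protocol's scope sentence carries one extra adjective: "The definition of severe symptomatic hypoglycemia includes all episodes in which neurological impairment was severe enough to prevent self-treatment".

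SAP 2.1.4.1 then turns the definition into a data rule with two conditions joined by *and*: "ticked “Subject was Not Capable of Treating Self and Required Assistance” to the question “Countermeasure Administration” and" "ticked “Yes” to the question “Were Symptoms Present".

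The rules for documented symptomatic, asymptomatic, probable symptomatic and relative hypoglycemia each begin with the opposite assistance condition. For asymptomatic hypoglycemia it reads "not ticked “Subject was Not Capable of Treating Self and Required Assistance” to the question “Countermeasure Administration” and".

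SAP 2.4.5.1 uses the categories as follows: "The number (%) of patients with any hypoglycemia, severe hypoglycemia and documented symptomatic hypoglycemia will be summarized respectively by treatment group". The same section adds two incidence rates, summaries by gender, age, race and antibody status, a Kaplan-Meier curve for the first severe or documented symptomatic event, and a listing of all reported events with category flags.

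**The concern.** The data rule is narrower than the definition it implements. By definition, an event in which the patient could not treat himself or herself and needed help is severe. Under the rule it is severe only if a second item was also answered Yes. Because the other four rules exclude assisted events, an event that fails the symptom condition does not move to a milder category. It gets no category at all.

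Severe hypoglycemia is the most serious of the five categories. A single uncategorised event would be absent from the severe count, from both severe rates, from the subgroup summaries and from the Kaplan-Meier curve, while still appearing in the listing. The report could then disagree with itself. The SAP also handles other missing safety data in the cautious direction, so an omission here would run against its own practice.

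**Working it through.** This is a question of classification logic. The plan states no figure to reproduce.

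**Inputs.** The five eCRF rules in SAP 2.1.4.1:

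| Category | Assistance box | Symptoms | Glucose | Other |
|---|---|---|---|---|
| Severe | ticked | Yes | any | none |
| Documented symptomatic | not ticked | Yes | ≤70 mg/dL | none |
| Asymptomatic | not ticked | No | ≤70 mg/dL | none |
| Probable symptomatic | not ticked | Yes | no value | countermeasure given, with improvement |
| Relative | not ticked | Yes | >70 mg/dL | none |

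**Step 1: assisted events under the rules as written.** With the assistance box ticked, only the severe row can apply. The symptom item has three states (Yes, No, blank) and glucose has three (≤70, >70, not measured), giving 3 × 3 = 9 combinations.

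| Symptoms | ≤70 | >70 | Not measured |
|---|---|---|---|
| Yes | severe | severe | severe |
| No | no category | no category | no category |
| Blank | no category | no category | no category |

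Three of the 9 are classified and 6 are not, whatever the countermeasure and recovery answers. The 6 include an assisted event with measured glucose at or below 70 mg/dL and symptoms answered No. These counts describe combinations of answers, not expected proportions of events.

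**Step 2: without the symptom condition in the severe row.** All 9 assisted combinations become severe and 0 are left out. No unassisted event changes category. Some unassisted combinations are also uncategorised, but that is a separate matter.

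**Step 3: does another rule close the gap?** SAP 2.5.3 has hypoglycemia rules for missing onset dates and times and for missing treatment dates, but none for a blank symptom item. Its general rule treats a derived variable as missing when a required input is missing, which for a blank symptom item leads to the same result. By contrast, SAP 2.4.5.2 and 2.5.3 class an event of uncertain onset as treatment-emergent, and SAP 2.5.3 assumes that an event with missing causality is related.

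**Step 4: what is lost and what is kept.** The event leaves the severe counts, the rates and the Kaplan-Meier curve of SAP 2.4.5.1. It stays in the listing. It may count as any hypoglycemia, because SAP 2.1.4.1 identifies hypoglycemia by entry on the dedicated form. That is not certain, because Protocol 11.4.3.1 builds its overall table from the five categories.

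**Step 5: illustration of size.** With the planned 60 patients in a dose arm, one patient dropped turns 1/60 = 1.7% into 0/60. With 30 on pooled placebo, it turns 1/30 = 3.3% into 0/30. These figures show what one event weighs. They are not a forecast.

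**The case against.** The strongest reply is that a correctly recorded severe event is never lost. A reader might infer that the rule misses, say, a patient found unresponsive who recalls no warning signs. The documents do not support that. Protocol 10.6.1 and SAP 2.1.4.1 both list seizures, unconsciousness and coma among the symptoms of hypoglycemia, and the item asks whether symptoms were present, not whether the patient remembers them. That patient is a Yes and is classified as severe. More generally, impairment that prevents self-treatment is itself symptomatic. The protocol's extra adjective and the SAP's reference to a page for symptomatic events point the same way, and Protocol 7.2.1 excludes patients with hypoglycemic unawareness. This stands: what remains is mainly inconsistent or incomplete data entry.

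Such entries can also be queried under Protocol 13.4, and the form may enforce an answer. The eCRF specification is not among the documents, so how easily the item can be left blank cannot be checked. An assisted event with no category flag would be visible in the listing, and events with seizure, unconsciousness or coma must be reported as SAEs. A reader who concluded that the event vanishes from the report would therefore be wrong. Safety analysis is essentially descriptive, so no planned test depends on this category.

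Finally, the symptom condition gives some protection against a mis-ticked box or help given when it was not needed. The wording of the box already covers the second case. The first is a real, small cost of changing the rule.

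None of this says how the severe table should treat an assisted event whose symptom item is still No or blank at lock. The SAP leaves that open, and its literal rule drops the event.

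**Conclusion.** The gap is certain as a matter of logic: 6 of the 9 assisted combinations have no category, and no other SAP rule assigns one. Its practical reach is narrow. It concerns assisted events with the symptom item answered No or left blank, and it affects the severe counts, rates, subgroup summaries and Kaplan-Meier curve, not the listing or SAE reporting. The numerical effect cannot be estimated, because the documents give no frequency for such entries, and the 1.7% and 3.3% figures assume exactly one affected patient. The conclusion rests on reading the rules literally and on there being no repair in the eCRF specification, which was not available. The priority is minor: a clarification worth making because it is cheap and because it brings the rule into line with the definition.

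**What to change.** In SAP 2.1.4.1, identify severe hypoglycemia by the assistance item and remove the symptom condition from that rule. Add that every assisted event with symptoms answered No or left blank is queried before database lock. If the site confirms the assistance tick, or the query is unresolved at lock, the event counts as severe. If the site corrects the tick, the event is classified under the remaining rules from the corrected entries.

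This takes a line or two of SAP text, a matching change in the derivation code and one data query. It needs no new data and leaves patient management and the classification of unassisted events unchanged. The downside is that a mis-tick of the assistance box that is never corrected would be counted as severe. That error is on the cautious side and would be visible in the listing.
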